10.4.4 Safety Analyses

The safety endpoint will be assessed at the 3-month ambulatory visit and includes:

- (1) fall-related injury (operationalized as any fall requiring acute medical care)
- (2) hospitalization for acute coronary syndrome
- (3) hospitalization for unstable arrhythmia

Separately, among intervention participants, study staff will monitor potential exercise-related adverse events on an ongoing basis and report any related AEs to the Principal Investigator. Points of contact will include weekly phone calls with the exercise therapist as well as electronic communication via the mHealth app which is checked daily.

In order to reduce the likelihood of these events, participants will complete the baseline 6MWT in-hospital; if any adverse event occurs during 6MWT (drop in SBP ≥ 15 mmHg, chest pain, ventricular arrhythmia),

CONFIDENTIAL

This material is the property of the NYU School of Medicine and Langone Medical Center. Do not disclose or use except as authorized in writing by the study sponsor

participants will be removed (not randomized). Other exclusion criteria (severe osteoarthritis, recent joint replacement, moderate or severe cognitive impairment) are also intended to minimize risk.

All adverse events will be reported directly to the Principal Investigator and to the DSMB, as outlined in Section 8, Assessment of Safety. Each adverse event will be counted only once for a given participant. Events will be described by start date, stop date, severity, relationship, outcome, and duration. If it is determined that the adverse event precludes further participation in the study among patients in the intervention arm, the study intervention will be discontinued, but participant data will be analyzed using the intention-to-treat principle.

For analysis of the safety endpoint between intervention and control arms, a two-sided significance test with two-sided confidence intervals will be performed (as with the efficacy endpoints).

10.4.5 Adherence and Retention Analyses

Adherence (termed engagement in our study, which is more reflective of patients' use of mHealth interventions) is a prespecified endpoint in our trial. To measure engagement with the assigned treatment strategy we will perform the following analyses:

- (1) Engagement with mHealth-CR: The mHealth-CR intervention includes a number of activities expected of participants randomized to this arm. The primary engagement endpoint is an 11-point score, tabulated weekly, indicating completion of each component of the mHealth-CR intervention: (1–7) daily entry of exercise data and rated perceived exertion (1 point for each day with total possible 7 points per week); (8) completed phone call with exercise therapist; (9) at least one electronic communication with exercise therapist; (10) watching educational video (which will vary by week); and (11) at least one home BP measurement. Engagement will be assessed as a pseudo-continuous outcome, as the score can range from 0% (0 activities completed) to 100% (all 11 activities completed).

Participant engagement is a primary endpoint of the study. We will conduct latent class analysis to identify profiles of engagement and explore whether these factors indicate membership in a class; these models use maximum likelihood estimation, implemented with the iterative EM algorithm, to identify a latent class solution for the set of indicators. We will evaluate model fit using the G2 statistic and compare models with the likelihood-difference test for nested models and the Akaike and Bayesian information criteria (AIC, BIC) for non-nested models. While we have identified four potential classes a priori, we will use the parametric bootstrap likelihood ratio test to select the optimal number of classes supported by the data in conjunction with the AIC and BIC. The output of the model will be a set of "item-response" probabilities giving the likelihood of a particular characteristic within each latent class, and a set of posterior predicted probabilities of latent class membership; uncertainty in predicting class membership will be summarized using the odds of correct classification (OCC) diagnostic tool.

To elucidate barriers to participation, we will use procedures that focus on developing coding protocols to highlight issues, problems, and potential recommendations. The goals of these analyses are to identify key barriers and facilitators, as well as any emerging themes related to the use of mHealth-CR to improve functional recovery and other patient-centered outcomes. Focus groups and interviews will employ semi-structured interview guides. Two independent viewers will record, transcribe, and code sessions. Coding will involve breaking responses into discrete units (e.g., sentences, phrases) and categorizing concepts into thematic groups. Discrepancies in coding will be resolved by reaching consensus among two investigators.

- (2) Receipt of traditional CR: Participants in both arms will receive standard referral to traditional (ambulatory) CR. We will summarize the uptake of this referral using attendance at initial and subsequent CR program visits.

CONFIDENTIAL

This material is the property of the NYU School of Medicine and Langone Medical Center. Do not disclose or use except as authorized in writing by the study sponsor

10.4.6 Baseline Descriptive Statistics

An enrollment summary will be provided giving the total number of enrolled patients by participating hospital, with both monthly and cumulative totals provided on an ongoing basis. Baseline demographic and clinical characteristics will be tabulated by hospital for the ITT population.

10.4.7 Planned Interim Analysis

There are no formal interim statistical analyses planned. The intervention (cardiac rehabilitation) has known benefits; the novelty of our trial is the delivery system for the intervention, which we anticipate will only have the (relatively low) risk of adverse events associated with exercise. In addition, the full sample size is needed to provide necessary information to achieve the study objectives.

10.4.7.1 Safety Review

Termination of the study intervention will occur when risks are posed to participants. Safety endpoints (designed to incorporate major risks) include fall-related injury requiring medical care (inpatient hospitalization) that occurs during study-directed exercise, hospitalization for acute coronary syndrome, or hospitalization for unstable arrhythmia.

Safety review will be performed independently by the DSMB. All adverse events will be reported to the DSMB and reviewed by the Principal Investigator on an ongoing basis. The procedure and scope of the safety monitoring parameters will be determined by the DSMB.

10.4.7.2 Efficacy Review

Not applicable as no interim analyses planned.

10.4.8 Additional Sub-Group Analyses

We will perform exploratory analyses stratified by sex race, and ethnicity, in order to investigate these characteristics as mediators of our endpoints.

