4.2.2 Secondary Study Endpoints

Protocol-defined secondary endpoints are: (1) goal attainment, as measured by goal attainment scaling (GAS); (2) change in participant reported health status: general (SF-12) and disease specific (SAQ-7); (3) change in activities of daily living (ADLs); (4) hospital readmission; and (5) death, in participants receiving mHealth-CR versus usual care.

- *Goal attainment*, defined as whether a person's individual functional goals are achieved as a result of the study intervention, will be measured using a 5-point goal attainment scale (GAS). Using the SMART goal framework,⁶³ GAS describes the person's expected level of goal achievement over 3 months, ranging from no change (scored as -2) to much better than expected (scored as +2). Scales are dynamically set according to a person's needs, while measurement of attainment is standardized. Goal attainment, through goal setting, is an especially important outcome in older adults who may begin an intervention with a variety of deficits (therefore necessitating individualized therapy towards realistic goals).⁶⁴
- *Participant reported health status* is measured using the SF-12⁶⁵ (general health status) and Seattle Angina Questionnaire 7 (SAQ-7)⁶⁶ (disease-specific health status). Health status encompasses a person's functional status, symptoms, and well-being, and is increasingly recognized as an important patient-centered outcome.^{67,68} Both the SF-12 and SAQ-7 have been validated and are convenient for participants (<5 minutes to administer). For the SF-12, we will analyze change from baseline to 3 months using a threshold of 5 points in SF-12 physical component score (PCS) as a clinically meaningful change.⁶⁹ For SAQ-7, we will analyze at a single time point (3 months) the number of participants who have residual angina (SAQ-7<100) vs. no angina (SAQ-7=100).⁶⁶
- *Change in ADLs* is defined as any improvement or worsening in basic (BADLs) or instrumental (IADLs) activities of daily living over 3 months. BADLs are basic self-care behaviors: feeding, toileting, bathing, dressing, and ambulating.⁷⁰ IADLs are activities that allow a person to live independently (e.g. food preparation, medication management, transportation, shopping, managing finances, using the telephone, and housekeeping).⁷⁰ ADL preservation is repeatedly cited by older adults as an important outcome,⁹ and prior research has shown that many patients with IHD experience ADL decline after hospitalization.⁷¹

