10.4 Description of Statistical Methods

10.4.1 General Approach

Statistical comparisons will be performed using two-sided significance tests and two-sided confidence intervals. We will begin all analyses with descriptive summary statistics and graphical displays of all variables, with attention to assessing balance in these characteristics by intervention group, and with assessment of the distribution of variables, relevant to the choice of statistical tests.

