10.4.2 Analysis of the Primary Efficacy Endpoint(s)

6MWD

We will assess the difference in 6MWD by calculating difference scores for each participant and comparing the intervention and usual care groups with an independent group t-tests allowing for unequal variances. We will also regress 3-month 6MWD on a binary indicator of treatment group, with adjustment for baseline 6MWD and the stratification factor (enrollment site). While randomization should obviate the need for additional adjustment, we will explore whether adjustment for participant-level characteristics (e.g., demographic factors or referral to ambulatory CR) is necessary, using the change-in-estimate criterion. We realize that engagement with the mHealth-CR program may also affect attendance and engagement with structured ambulatory CR programs. We intend to explore this as a mediator of the effect of assignment to the intervention arm. We will use structural equation models to estimate the direct and indirect effects of mHealth, where the direct effect is that of mHealth-CR on the 6MWD, and the indirect effect is mediated through attendance at structured ambulatory CR.

Engagement

We hypothesize that (1) among participants offered mHealth-CR, there will be distinct trajectories of engagement (e.g., sustained engagement, disengagement, reengagement, deteriorating engagement); and (2) there will be significant differences in participant characteristics among these groups. While our aim is largely exploratory (given the paucity of data on mHealth-CR engagement), we will test whether the following characteristics are significant: age (≥ 80 years), sex, race/ethnicity, comorbidity burden (≥ 2 chronic medical conditions), frailty, social support (based on living alone), cognitive impairment (based on Mini-Cog), and depressive symptoms (based on PHQ-8). We selected these factors based on literature related to engagement in other technologies. We will conduct latent class analysis to identify profiles of engagement and explore whether these factors indicate membership in a class; these models use maximum likelihood estimation,

CONFIDENTIAL

This material is the property of the NYU School of Medicine and Langone Medical Center. Do not disclose or use except as authorized in writing by the study sponsor

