10.4.3 Analysis of the Secondary Endpoint(s)

Analysis of secondary efficacy endpoints will proceed in a similar fashion to the primary endpoints:

Goal attainment will be assessed at baseline and 3 months. At baseline, participants will set 1 personal goal related to improving daily function or symptom control (e.g., walking with less dyspnea, attending family functions). At 3 months, goal attainment will be rated using a 5-point GAS, scored as follows: no change from baseline (-2); less than expected (-1), expected (0), better than expected (+1), and much better than expected (+2). To preserve the ordinal nature of the data, we will calculate a median GAS score (-2 to +2) for each participant, and then compare the treatment and control groups using a Wilcoxon-Mann-Whitney rank-sum test.⁸⁹ Secondly, we will transform each participant’s GAS score into a single aggregated T-score using the standardized formula: $T = 50 + ([10\sum(w_i x_i)] / [(1-\rho)(\sum w_i)^2 + \rho(\sum w_i)^2]^{1/2})$, where w_i = weight assigned to the goal; x_i = the attained score for the goal (-2 to +2); and ρ = the expected correlation of the goal scales, commonly estimated to be 0.3. For this study, all weights will be assigned a value of 1 (i.e., all goals are weighted equally). A T-score of 50 indicates that on average the expected level of goal attainment was achieved.¹² We will then compare mean T-scores for treatment and control groups at 3 months using a two-sample t-test. We will also compare the percentage of participants in the treatment and control groups who met their expected level of goal attainment on at least 1 goal using a chi-square test.

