with our expected sample of 320 patients, using two-sided, 0.05-level tests; we will not implement multiple comparisons correction for these secondary outcomes. Baseline event rates and standard deviations are estimated from the literature.¹¹⁵⁻¹¹⁸ For example, we have 90% power to detect a difference between groups of 5 units in the SF-12 score.

All comparisons between the randomized groups in this trial will be performed according to the principle of "intention-to-treat"; that is, participants will be analyzed according to the treatment group to which they were randomized, regardless of subsequent crossover. The intent-to-treat (ITT) population will include all subjects who receive a randomized treatment assignment, except for those with a documented violation of trial eligibility criteria.

The table below shows clinically meaningful effect sizes for secondary efficacy outcomes, and gives the power to detect these effect sizes with our expected sample of 320 patients, using two-sided, 0.05-level tests; we will not implement multiple comparisons correction for these secondary outcomes.

Outcome	Endpoint definition	Effect size	Estimated s.d.	Power
Goal attainment scaling	GAS score	5	15	73%
Health status	SF-12	5	12	90%
Health status	Residual angina on SAQ	15-20%	n/a	67-93%
ADLs	Standardized ADL score	15-20%	1	64-87%
Hospital readmission	Admission by 3 months	15%	n/a	91%
Death	Death by 3 months	10%	n/a	82%

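### Minor, exploratory only: 10.4.8 calls sex, race and ethnicity mediators and plans stratified analysis without committing to a treatment-by-subgroup estimate for any between-arm endpoint

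*Combined protocol and SAP*

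**What the plan says.** Section 10.4.8 is a single sentence. It plans exploratory analyses stratified by sex, race and ethnicity, "in order to investigate these characteristics as mediators of our endpoints". It names no endpoint, no model and no way of comparing the strata.

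The between-arm models elsewhere are these:

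- **10.4.2 (6MWD):** a t-test on change scores, and a regression of 3-month 6MWD on treatment, baseline 6MWD and site. Demographic factors appear only as possible adjustment covariates, chosen by the change-in-estimate criterion.
- **10.4.3 (secondary endpoints):** rank-sum, t and chi-square tests for goal attainment, regression on treatment and baseline for health status, a longitudinal model for ADLs, and logrank and Cox analyses for readmission and death. Confounder adjustment is optional.

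None of these has a treatment-by-subgroup term. For comparisons in general, 10.4.1 says: "Statistical comparisons will be performed using two-sided significance tests and two-sided confidence intervals".

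Two other uses bear on the reading. Section 10.4.2 says of attendance at ambulatory CR, "We intend to explore this as a mediator of the effect of assignment to the intervention arm", with direct and indirect effects from structural equation models. For engagement, the same section says "we will test whether the following characteristics are significant" and lists sex and race/ethnicity among them, but only for participants offered mHealth-CR.

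**The concern.** A mediator lies on the path from assignment to outcome, so it must be something that assignment can change. Ambulatory CR attendance qualifies. Sex, race and ethnicity do not. The word in 10.4.8 is probably a slip for moderators, but as written the sentence names a quantity that does not exist for these traits.

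The method matters more. If the question is whether mHealth-CR works differently in women and men, the answer is the difference between the two effects, with its confidence interval. Stratified results alone are one estimate, interval and p-value per stratum. The plan does not say that the difference will be reported or how it will be read. Neither multiplicity statement fills the gap: 10.4.9 concerns the single primary efficacy endpoint, and 10.5 says of the secondary outcomes, "we will not implement multiple comparisons correction for these secondary outcomes".

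What is at stake is the reading of exploratory subgroup results. Section 5.4 sets recruitment targets for women and for nonwhite, black and Hispanic participants, so readers are likely to look at these results.

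**Working it through.** **Inputs.** From 10.5: 240 intervention and 80 usual-care participants evaluable, SD of change in 6MWD 60 m, two-sided alpha 0.05, difference of interest 25 m. From 5.4: at least 40% women, 19% nonwhite, 12% black and 12% Hispanic. Assumptions of this check: each share sits at its minimum and is the same in both arms, the SD is 60 m in every stratum, and each characteristic is a two-level split. Power uses the normal approximation.

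**The plan's own figure.** Section 10.4.8 gives none, so start from the primary comparison in 10.5.

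- SE = 60 × √(1/240 + 1/80) = 7.75 m.
- Power for 25 m = Φ(25/7.75 − 1.96) = 89.8%, against a stated value of about 90%.
- Power for 22 m = 81.1%, against a stated 80%.

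Both agree with the plan.

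**Treatment-by-sex contrast on change scores.** Stratum SE = 60 × √(1/n₁ + 1/n₀).

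- Women, 96 and 32: 60 × √(1/96 + 1/32) = 12.25 m.
- Men, 144 and 48: 60 × √(1/144 + 1/48) = 10.00 m.
- SE of the difference between effects = √(12.25² + 10.00²) = 15.8 m, about twice the SE of the overall effect.
- 95% CI half-width = 1.96 × 15.8 = 31 m.
- Power for a 25 m difference in effect = Φ(25/15.81 − 1.96) + Φ(−25/15.81 − 1.96) = 35%.
- Difference detectable with 80% power = 15.81 × (1.960 + 0.842) = 44 m.

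**All three shares, same formulas:**

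| Smaller subgroup | Intervention / usual care in it | Stratum SEs (m) | SE of difference (m) | Power for 25 m | 80% power at |
|---|---|---|---|---|---|
| 40% (women) | 96 / 32 | 12.25, 10.00 | 15.8 | 35% | 44 m |
| 19% (nonwhite) | 45.6 / 15.2 | 17.77, 8.61 | 19.7 | 24% | 55 m |
| 12% (black or Hispanic) | 28.8 / 9.6 | 22.36, 8.26 | 23.8 | 18% | 67 m |

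The last row rests on about 10 evaluable usual-care participants (80 × 0.12 = 9.6), so the coding of race decides whether a term can be estimated usefully.

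The baseline-adjusted regression may be somewhat more precise. The documents give no residual SD, so no figure is offered for it.

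**Why within-stratum p-values should not be compared (illustration only).** Suppose the true effect is 25 m in both sexes. Power is then Φ(25/12.25 − 1.96) = 53% in women and Φ(25/10.00 − 1.96) = 71% in men. The chance that exactly one sex is significant is 0.532 × 0.295 + 0.468 × 0.705 = 0.49, with no effect modification present.

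**The case against.** The best defence is that this is one sentence about exploratory work, and much of the criticism is drawn from its silence. Correcting the term is a one-word edit. A stratified analysis can include a comparison of strata, and nothing in 10.4.8 forbids it. The intervals promised in 10.4.1 would let a reader work out an unadjusted difference. The text also says mediators of the endpoints, not of the treatment effect, so a looser aim, such as finding determinants of outcome, is possible. Finally, the interaction estimates will often be inconclusive.

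Most of this limits the point without removing it. The plan cannot be said to exclude an estimate of the difference; it only fails to commit to one. Effect modification is the likeliest aim, not a certain one. Low precision is a reason to show the interval, since separate stratum results hide it.

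Four stronger readings are tempting, and the documents do not support them:

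- **The authors will infer a subgroup difference from one significant and one non-significant stratum.** The plan never proposes this, so the 49% figure is not an error rate of the plan.
- **The plan launches many uncorrected subgroup tests.** Section 10.4.8 names no endpoints, so no count can be attributed to it.
- **A formal mediation analysis of sex or race is intended.** The structural equation models in 10.4.2 concern CR attendance only.
- **Sex and race are never tested.** Section 10.4.2 relates them to engagement class. That analysis is confined to the intervention arm and lies outside this point.

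**Conclusion.** The point holds as a minor one. *Mediators* is the wrong term for characteristics fixed before randomisation, and the plan does not commit to estimating how the treatment effect differs between strata for any between-arm endpoint. No primary or secondary conclusion depends on 10.4.8.

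The size of the issue is the imprecision that separate stratum results would leave unstated: SEs of 15.8, 19.7 and 23.8 m for the difference in effect, against a target effect of 25 m. These figures rest on the protocol's SD of 60 m applied to every stratum, 240 and 80 evaluable participants, and subgroup shares at the recruitment minimums. Shares above the minimums and below half would improve precision. The finding about wording and method does not depend on these figures.

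**What to change.** In 10.4.8:

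1. Replace *mediators* with *effect modifiers (moderators)*, after confirming that this is the aim.
2. For 6MWD, add treatment-by-sex, treatment-by-race and treatment-by-ethnicity terms, with the matching main effects, to the baseline- and site-adjusted regression in 10.4.2. Take each characteristic in turn.
3. State the race coding in advance, for example white versus nonwhite, given about 10 evaluable usual-care participants in a 12% subgroup.
4. Report interaction and subgroup estimates with 95% CIs, labelled exploratory and not adjusted for multiplicity.
5. State that no subgroup claim will be made from within-stratum p-values, and that a non-significant interaction is not evidence of equal effects.

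The cost is a few sentences and product terms in a regression already planned. No new data are needed, and the primary test, alpha and sample size stay as they are. The downside is that the estimates will be imprecise and often inconclusive.
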